1.2 Background Information on IgPro20

1.2.1 Overview

IgPro20 is a ready-to-use formulation of polyvalent SCIG. The IgG portion represents all IgG subclasses present in human plasma and retains all IgG function (ie, Fc receptor interaction site [Fc] and antigen binding fragment [Fab] mediated activity). The sterile 20% IgG solution is stabilized with 250 mmol/L L-proline at pH 4.8. IgPro20 also contains 8 to 30 mg/L polysorbate 80 (P80). IgPro20 has a low sodium content (< 10 mmol/L) and an osmolality of approximately 390 mOsmol/kg.

The protein moiety of IgPro20 is highly purified IgG ($\geq 98\%$ purity). More than 90% of the IgG consists of monomers and dimers. IgPro20 is prepared from large donor pools and represents the antibody spectrum present in the donor population. Careful selection of donors, as well as testing of each individual donation and the plasma pool for viral markers, helps to ensure viral safety of the finished product.

The manufacturing process (IgG isolation) for IgPro20 is based on the manufacturing process for Privigen® (IgPro10). After production of the active substance solution, the final IgPro20 product is formulated and concentrated to the higher protein content of 20%.

IgPro20 was approved for PID in the US, the EU, Canada, Switzerland, Japan, Australia, and several other countries under the trade name Hizentra.

1.2.2 Nonclinical Evaluation

Human immunoglobulins are naturally occurring proteins with a well-established safety and tolerability record. The testing of human immunoglobulin preparations in animal models is of limited value because immunoglobulins are immunologically active and can cross-react between species. Nonclinical studies with IgPro20 focused on its SC use (local tolerance, PK), functionality (in vitro Fab and Fc function, in vivo efficacy in experimental allergic encephalomyelitis [EAE] rat model), safety regarding hypotensive effects, and repeated SC administrations.

Fab and Fc functions of IgPro20 are comparable to those of Privigen and other marketed IVIG products. In the EAE rat model (a nonclinical model of human multiple sclerosis) IgPro20 administered SC attenuated the symptoms of EAE and led to a lower mortality.

The bioavailability of IgPro20 was assessed after SC administration to rats on 5 consecutive days; a dose-dependent increase in area under the concentration-time curve (AUC) and maximum serum concentration of human IgG was found. In 2 repeated-dose toxicity studies in rats with SC administration of IgPro20 every other day for 28 days and 6 months, respectively, all animals developed antibodies against human IgG in a dose dependent manner. In spite of this antibody formation, human IgG was detected in the serum of the animals; serum concentrations increased to a steady-state (28-day study) with a slight decline in the second half of the in-life phase of the 6 months study. Thus antibody development against human IgG did not result in total removal of human IgG from the blood of the animals. The highest dose administered in this study resulted in IgG serum levels in the animals that are comparable to IgG levels obtained in patients treated with IgPro20, and was considered a no observed adverse effect level.

IgPro20 was also tolerated locally after SC, IV, paravenous, and intra-arterial application in rabbits.

IgPro20 contains 250 mmol/L of the non-essential amino acid L-proline as a stabilizer. Studies on L-proline in safety pharmacology, multiple dose toxicity, reproduction toxicity and in juvenile animals were conducted during development of Privigen. Studies with IV and SC administration of L-proline were included. L-proline is a suitable excipient of IVIGs at

the specified concentrations which was confirmed in clinical studies conducted with Privigen. These results were confirmed in a 28-day repeated-dose toxicity study in rats with daily SC administration of L-proline performed during IgPro20 development. Considering the lower amount of L-proline infused with IgPro20 compared with Privigen, due to smaller doses in average weekly SCIG vs. average 3- or 4-weekly IVIG dosing regimens and the good tolerability of IgPro20 administered SC to rabbits, it can be concluded that L-proline can be safely used as an excipient in IgPro20.

1.2.3 Previous Clinical Experience

The approval of IgPro20 for the treatment of patients with PID was based on data from 3 pivotal studies in the US, Europe, and Japan (ie, studies ZLB04_009CR, ZLB06_001CR, and ZLB06_002CR, respectively). In addition, extension studies to the 3 aforementioned phase 3 pivotal studies have been conducted and completed: 1 study each in the US (US extension study IgPro20_3001), in Europe (European extension study ZLB07_002CR), and in Japan (follow-up study ZLB07_001CR). A further long-term extension study in Japan (IgPro20_3006) has also been completed.

1.2.3.1 Phase 3 PID Study ZLB04_009CR (US Pivotal Study)

This prospective, open-label, phase 3 study was conducted in the US and investigated the efficacy, safety, local tolerability, and PK of SC IgPro20 in 49 subjects with PID. Subjects previously receiving monthly treatment with IVIG were switched to weekly SC administration of IgPro20 for 15 months. Subjects were initially treated with 1.30 times their previous IVIG dose during a 12-week wash-in/wash-out period and had their IgPro20 dose further adjusted based on the results of the PK substudy for the subsequent 12 month efficacy period. Doses were adjusted to ensure equivalent systemic IgG exposure to IVIG as measured by the serum IgG AUC.

The primary efficacy variable was the annualized rate of serious bacterial infections (SBIs, as defined in the Food and Drug Administration [FDA] Guidance for Industry [FDA, 2013]). None of the subjects had an SBI and the annualized rate of total infections per subject was 2.76. Overall, SC infusions with IgPro20 provided a high level of efficacy in subjects with PID in terms of passive immunity and maintaining adequate and consistent serum IgG levels. There were no safety concerns with the use of IgPro20.

1.2.3.2 Phase 3 PID Study ZLB06_001CR (European Pivotal Study)

This prospective, open-label phase 3 study was conducted in Europe that investigated the efficacy, safety, tolerability, and PK of SC IgPro20 in 51 subjects with PID. The study consisted of a 12-week wash-in/wash-out followed by a 28-week efficacy period. The IgPro20 weekly doses administered during this study were generally equal to the subjects' previous weekly equivalent IVIG or SCIG doses. The primary efficacy variable was a descriptive comparison of IgG trough levels at 6 consecutive weeks at steady-state within the study. During the study, the mean of individual median IgG trough levels increased by 8.1% with IgPro20 treatment (from 7.49 g/L with the previous IgG therapy to 8.10 g/L during Infusions 12 to 17). None of the subjects had an SBI during the efficacy period of this study (after washout of the previous IgG product), and only one subject had an SBI during the wash-in/wash-out period, resulting in an annualized rate of 0.03 SBIs/subject. The annualized rate of total infections was 5.18 infections/subject. Overall, it was demonstrated that SCIG therapy with IgPro20 is a highly effective treatment for adult and pediatric subjects with PID when administered at approximately 100% of the weekly equivalent doses during the subjects' preceding therapy. There were no safety concerns with the use of IgPro20.

1.2.3.3 Phase 3 PID study ZLB06_002CR (Japan Pivotal Study)

This phase 3 study was conducted in Japan including 25 subjects, with a PK sub-study including 8 subjects, to investigate the efficacy, safety, tolerability, and PK of IgPro20 in subjects with PID. The weekly dose of IgPro20 was the weekly equivalent dose of the previous IVIG treatment, and IgPro20 treatment included a 12-week wash-in/wash-out period followed by a 12-week efficacy period. The primary efficacy variable was maintenance of the mean of individual median IgG concentration at trough level (C_{trough}) values expressed via the ratio of geometric mean concentrations. IgG C_{trough} values increased by 9% with IgPro20 treatment, from 6.53 g/L in the IVIG period to 7.15 g/L during the SCIG efficacy period, meeting the primary objective. IgG C_{trough} values <5 g/L on IgPro20 therapy during the Japan pivotal study were seen in only 1 of 24 subjects. In this study, none of the subjects had an SBI. A total of 52.4% of subjects had an infection in the efficacy period, resulting in an annualized rate of 2.98 infections/subject. Overall, it was demonstrated that SCIG therapy with IgPro20 is an effective treatment for adult and pediatric subjects with PID in Japan when

administered at approximately 100% of the weekly equivalent doses of the subjects' preceding IVIG therapy. There were no safety concerns with the use of IgPro20.

Long-term extension and follow-up studies, as outlined in [Section 1.2.3](#), have further confirmed the high efficacy and safety of IgPro20 at steady-state dosing. In addition to safety data from the clinical development program, postmarketing experience with IgPro20 has shown the product to be well tolerated, with a similar safety profile in pediatric and geriatric patients as documented for adult patients.

1.3 Study Overview

This is a multicenter, open-label, parallel-arm, non-randomized study designed to evaluate safety and tolerability of higher infusion parameters of IgPro20 in subjects with PID.

The primary objective of this study is to characterize the responder rate at higher infusion parameters of IgPro20. Subjects will be assigned to 1 of 3 treatment cohorts: Pump-Assisted administration with 3 upward volume titrations (25 mL, 40 mL, and 50 mL); Pump-Assisted administration with 4 upward flow rates per injection site (25 mL/h, 50 mL/h, 75 mL/h and 100 mL/h) and Manual Push administration (manual infusion using syringe without a pump) with upward titration of flow rate per injection site of 30 mL/h, 60 mL/h, and 120 mL/h (0.5 mL/min, 1 mL/min, and 2 mL/min, correspondingly).

Further details of the study design can be found in [Section 3](#).

1.4 Potential Risks and Benefits

Safety data from the 3 pivotal studies performed by CSL for the authorization of IgPro20 in PID showed that almost all adverse events (AEs) (99%) were mild or moderate in intensity. There was no dose-dependent increase in the overall rate of AEs, within the range of doses and flow rates tested in these studies, and there was no evidence in either study of severe systemic AEs.

Adverse reactions such as local reactions, headache, fatigue, nausea, pain, pruritus, rash, vomiting, and pyrexia were observed during the clinical development program. In addition, in the postmarketing setting, reactions such as hypersensitivity, tremor, and burning sensation were reported, as well as rare events such as anaphylaxis, aseptic meningitis syndrome and

thrombotic events. SC infusions generally result in lower rates of headache and other systemic adverse reactions than IV infusions, which is attributed to the more stable serum IgG concentrations attained with SCIG treatment.

The risk that products manufactured from plasma could transmit an infectious agent has been reduced by screening plasma donors for prior exposure to pathogens and by testing the donations for the presence of certain markers of infections. In addition, different complementary virus elimination processes used during the manufacture of IgPro20 (incubation at pH 4, virus filtration, fractionation, and depth filtration) effectively reduce the potential for viral transmission. The manufacturing process was also investigated for its capacity to eliminate hamster-adapted scrapie agent 263K, which is considered to be a model for Creutzfeldt-Jakob disease and variant Creutzfeldt-Jakob disease. The results demonstrated substantial removal of the infectious agent by the manufacturing process in all model systems. To date, no viral infection related to the infusion of IgPro20 was reported. However, the possibility of transmitting infective agents cannot be totally excluded.

As previously noted, Hizentra infusions at higher than currently approved volume and flow rate parameters per injection site have been used in both clinical research and clinical practice without apparent safety signals (see [Section 1.1.4](#) [SCIG Infusion Parameters]). However, there are insufficient data to allow for objective quantification of any potential increase in safety risks associated with these higher infusion parameters.

The benefits of manual push include the use of smaller volumes per infusion compared to less frequent infusion schedules. Other advantages associated with manual push include the ability to maintain more even serum IgG concentrations with higher trough levels compared to weekly or twice weekly schedules, which could potentially confer better protection against infections, as well as lower time per infusion and total time per weekly/monthly dose compared to pump-assisted infusions. The use of manual push is also associated with a simpler infusion technique (ie, there is no requirement to load and handle a pump) and reduced healthcare costs as there is no expenditure on a pump. The benefits of the higher flow rates and volumes, as proposed for the current study, include reduced infusion time, and fewer injection sites per infusion.

A number of disadvantages are associated with use of the manual push technique, including the difficulty to control the syringe to deliver a stable flow rate and the manual strength required to operate the syringe for several minutes.

Overall, the associated benefit-risk assessment of the study is considered acceptable for subjects enrolled in the study.

2. Study Objectives and Endpoints

2.1 Primary Objective and Endpoints

2.1.1 Primary Objective

The primary objective of this study is to determine the responder rate at higher infusion parameters of IgPro20 under the following conditions:

- Pump-Assisted: Volume per injection site of 25 mL, 40 mL, and 50 mL.
- Pump-Assisted: Flow rate per injection site of 25 mL/h, 50 mL/h, 75 mL/h and 100 mL/h.
- Manual Push (manual infusion using syringe without a pump): Flow rate per injection site of 30 mL/h, 60 mL/h, and 120 mL/h (0.5 mL/min, 1 mL/min, and 2 mL/min, correspondingly).

2.1.2 Primary Endpoints

The primary endpoints are as follows:

- Pump-Assisted Volume Cohort: Percentage of responders for each planned volume (ie, 25 mL, 40 mL and 50 mL per injection site).
- Pump-Assisted Flow Rate Cohort: Percentage of responders for each planned flow rate (ie, 25 mL/h, 50 mL/h, 75 mL/h and 100 mL/h per injection site).
- Manual Push Flow Rate Cohort: Percentage of responders for each planned flow rate (ie, 30 mL/h [0.5 mL/min], 60 mL/h [1 mL/min], and 120 mL/h [2 mL/min] per injection site).

2.2 Secondary Objectives and Endpoints

2.2.1 Secondary Objectives

The secondary objectives of the study are:

- To evaluate the safety of pump-assisted IgPro20 infusions at higher infusion parameters (volume and flow rate).
- To evaluate the safety of manual push IgPro20 infusions.
- To evaluate the tolerability of higher infusion parameters of IgPro20.

2.2.2 Secondary Endpoints

The secondary endpoints are as follows:

- The rate of total AEs per subject and per infusion by cohort and by each of the infusion parameter levels within the cohort.
- The rate of local reactions per subject and per infusion by cohort and by each of the infusion parameter levels within the cohort.
- The time to onset of local reactions per subject and per infusion by cohort and by each of the infusion parameter levels within the cohort.
- Severity of local reactions per subject and per infusion by cohort and by each of the infusion parameter levels within the cohort.
- Duration of local reactions per subject and per infusion by cohort and by each of the infusion parameter levels within the cohort.
- For all cohorts: Tolerability of a certain infusion parameter; ie, percentage of infusions per cohort by volume/flow rate subgroup experiencing no severe local reactions for each of the infusion parameter levels.

2.3 Exploratory Objective and Endpoints

2.3.1 Exploratory Objective

CCI

2.3.2 Exploratory Endpoints

CCI

3. Study Design

3.1 Study Design and Rationale

This multicenter, open-label, parallel-arm, non-randomized study is designed to evaluate safety and tolerability of higher infusion parameters of IgPro20 in subjects with PID. The study will include 3 cohorts with a minimum of 15 subjects each as follows:

- Pump-Assisted Volume Cohort (weekly infusions): Volume per injection site of 25 mL up to 50 mL.
- Pump-Assisted Flow Rate Cohort (weekly infusions): Flow rate per injection site of 25 mL/hour up to 100 mL/hour.
- Manual Push Flow Rate Cohort (2 to 7 infusions per week): Flow rate per injection site of 25 to 30 mL/hour up to 120 mL/hour (equivalent of approximately 0.5 mL/minute up to 2 mL/minute; see [Table 1](#)).

Each cohort will test 3 infusion parameter levels (for Pump-Assisted Flow Rate Cohort – 4) for at least 4 weeks each over a duration of 12 weeks (for Pump-Assisted Flow Rate Cohort – 16 weeks). After the fourth week on each level, qualifying subjects (responders) will switch to the next infusion parameter level (eg, from 25 to 50 mL/h). During the study the weekly dose will remain unchanged (as prescribed by treating healthcare provider, usually within 100-200 mg/kg per week range); only the respective infusion parameter under evaluation will change. If a subject is unable to tolerate the respective infusion parameter level (ie, is a non-responder at that level, for definition see [Section 11.3.5](#)), the subject will continue study

[figure not shown]
participation at the individually previously tolerated infusion parameter level for the remaining full study duration, to collect safety information.

If a subject within the Pump-Assisted Cohort is able to perform ≥ 3 out of 4 (75%) valid infusions at a certain infusion parameter level, he/she will be considered to be a responder for this infusion parameter level (eg, completed 3 infusions with 50 mL/h means responder for 50 mL/h). Valid infusions do not need to be consecutive. Determination of a responder in the Manual Push Cohort is more complex due to the expected variable frequency of infusions per week for different subjects (see [Section 11.3.5](#) for further details). Valid infusions in this cohort also do not need to be consecutive. However, each subject needs to adhere to the same schedule (number of infusions per week) throughout the study.

An infusion parameter will be considered successfully achieved if at least one third of the subjects in the corresponding cohort (5 of 15) are responders at that infusion parameter level, as defined above. The highest achieved infusion parameter level will be used for the label change. The rationale for this is based on medical experience (personal communications with several key opinion leaders and limited clinical research experience). A response rate for reaching the top infusion parameter for each endpoint of 50% is assumed. Using a binomial distribution with 15 evaluable subjects, there will be a 94% probability that the observed response rate for a single endpoint in the study is $\geq 33\%$.

Excluding the differences in infusion parameters/administration, all 3 cohorts have a similar overall study design (including AE collection). A schematic overview of the study is presented in [Figure 1](#).

Figure 1. Study Overview

3.2 Dose and Dosing Regimen

IgPro20 will be administered subcutaneously at a dose prescribed by subject’s healthcare provider prior to study entry (usually 100 to 200 mg/kg per week). Subjects in the Pump-Assisted Cohorts will administer weekly treatment and subjects in the Manual Push Cohort will administer more frequent infusions (ie, 2 to 7 times per week).

3.3 Planned Study Duration

The duration of the study for an individual subject is expected to be 3 months per subject in the Manual Push Flow Rate and Pump-Assisted Volume Cohorts, and 4 months in the Pump-Assisted Flow Rate Cohort. The overall study duration (ie, first subject’s Screening visit to last subject’s End of Study visit) will be approximately 18 months.

3.4 Planned Number of Sites

The study is planned to be conducted at approximately 15 sites in the US and Canada.

3.5 Planned Number of Subjects

Approximately 50 subjects will be enrolled into the study. A target of 45 evaluable subjects (ie, 15 subjects per cohort) is needed. Enrolled subjects will include a target of 14 (30%) pediatric subjects ≤ 17 years of age and a target of 9 (20%) obese subjects with BMI of ≥ 30

kg/m². Pediatric and obese subjects may be distributed across any or all of the treatment cohorts without respect to balanced enrollment within the cohorts for these subpopulations..

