1.1.3 Manual Push Technique

The conventional mode of SCIG administration has been an infusion pump, delivering IgG volumes of up to 25 mL per injection site, which can take up to 2 hours (Berger, 2008; Shapiro, 2010). Infusion pumps may be difficult to use for some patients and the potential costs might be unfavorable (Misbah et al, 2009). As an alternative, the manual push technique, also called rapid push, has been established in recent years for the administration of SCIG. It is a simple method where SCIG is given manually by injection using syringe and a short tubing with a butterfly needle. The total weekly dose is divided into several smaller doses, depending on each patient's dose and preference. Compared to weekly pump-assisted infusions, infusion times are much shorter, ranging from 5 to 20 minutes, and fewer injection sites are used. Furthermore, it provides effective and cost-efficient drug delivery, improved patient autonomy and convenience (Shapiro 2010; Shapiro 2013a; Martin et al, 2013). Based on a retrospective analysis comparing standard pump administration vs. rapid push

administration, it has been shown that serum IgG levels as well as the overall safety and tolerability profiles are comparable between the 2 SCIG infusion methods. In addition, manual push is well tolerated in both pediatric and obese adult patients and can be a practical treatment option in most PID patient subpopulations requiring SCIG replacement therapy, improving treatment satisfaction and supporting patient adherence (Shapiro 2013a; Misbah et al, 2009; Shapiro 2013b; Shapiro 2013c).

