1.1.4 SCIG Infusion Parameters

The currently approved Hizentra® infusion parameters in the United States (US) and abroad include a volume per injection site of up to 25 mL, and a flow rate of up to 25 mL/h per site (US package insert, European Union [EU] package insert), as outlined below:

Volume – For the first infusion of Hizentra, do not exceed a volume of 15 mL per injection site. The volume may be increased to 20 mL per site for the fifth infusion and then to 25 mL per site as tolerated.

Rate – For the first infusion of Hizentra, the recommended flow rate is 15 mL per hour per site. For subsequent infusions, the flow rate may be increased to 25 mL per hour per site as tolerated.

Higher infusion parameters, such as an increased flow rate and volume per injection site, reduce the time needed for infusion and decrease the number of injection sites, independent of the method used. An infusion of up to 60 mL per site and a flow rate of more than 60 mL/h using the manual push method have been previously described. In retrospective analyses of adult and pediatric patients using the rapid push method, the majority of subjects reported an infusion time of 9 minutes or less. With a mean volume per site of 15.8 mL in adults, an average flow rate of 1.75 mL/min or 105 mL/h can be assumed. In the age group of 10 to 18 years, an even higher flow rate of 1.9 mL/min (114 mL/h) can be assumed with a mean volume per site of 17.1 mL. Furthermore, in obese adults (body mass index [BMI] ≥ 30 kg/m²) a mean volume per site of 17.8 mL was documented, providing an average flow rate of 1.97 mL/min (118.67 mL/h) without tolerability issues (Shapiro 2013a; Shapiro 2013b; Shapiro 2013c).

While the flow rate in manual push is not usually presented in mL/h due to small volumes and short infusion times, a more detailed analysis of average flow rates, based on data from available publications, is presented in Table 1.

Table 1. Average Flow Rates in Manual Push Infusions

Manual push flow rate as originally reported	Flow rate, mL/min	Flow rate, mL/h	References
15 min per 3 mL	0.2	12	Berger, 2008.
1-2 cc/min	1-2	60-120	Misbah et al. 2009.
9 min per 15 mL	1.7	100	Shapiro, 2013b.
5 min per 10 mL	2	120	Richter et al., 2013.
9 min per 20 mL	2.2	133	Shapiro, 2013b.

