- c) For the Manual Push Flow Rate Cohort, a subject is considered as a ‘responder’ for a certain infusion parameter if he/she has performed $\geq k$ valid infusions (see a) for that infusion parameter in any order, ie, not necessarily consecutive) during the 4 weeks planned for that infusion parameter level, where k is specified in Table 7.

Table 7. Responder Requirements in Manual Push Cohort

Manual push infusions /wk	Infusions scheduled for parameter set (n)	Minimum No. of valid infusions (k)
2	8	5
3	12	7
4	16	10
5	20	12
6	24	15
7	28	17

- d) For each cohort (c) the percentage of subjects with response to a certain infusion parameter (p), $R_{c,p}$, will be calculated as [%]:
- $$100 * (\text{Number of responders for } p \text{ in cohort } c) / (\text{number of subjects from the Safety Population in cohort } c)$$
- where response is defined as outlined in b) and c), respectively.

The success criterion for any $R_{c,p}$ will be considered fulfilled if $R_{c,p} \geq 33\%$. Within each cohort, the highest infusion parameter with fulfilled success criterion will be considered the new top infusion parameter to be recommended for the Hizentra label. No formal statistical testing will be performed. All subjects included in the Safety Population of a cohort will be included in the denominator for calculation of $R_{c,p}$.

Rationale for number of valid infusions to qualify a responder in the manual push cohort: The probability for a subject to be a responder for a certain infusion parameter is assumed to be 50% irrespective of the value of the infusion parameter itself, ie, identical to the assumed response rate in [Section 11.1](#). This assumption is based on the expectation that there will be no infusion-related reasons for a subject to interrupt the infusion or change the infusion parameters. To achieve ≥ 3 out of 4 valid infusions the probability for a single infusion to be valid has to be $\geq 61\%$ for pump assisted cohorts. Using this 61% success probability for a single infusion in the manual push cohort the minimum of successes (k) in above table corresponds to a probability for a subject to be a responder of at least 50%.

The primary endpoints will be considered and evaluated independently from each other.

No imputation of missing data will be performed.

Descriptive subgroup analyses will be performed for Infusion Parameters by:

- Age class (≤ 17 years, > 17 years).
- BMI class ($< 30 \text{ kg/m}^2$, $\geq 30 \text{ kg/m}^2$).

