#### 8.2.9 Subgroups

The study design does not include any stratification factors, and there are no plans for post hoc stratification. There are no formal plans for investigating any covariates.

The analysis of infusion parameters will be presented stratified by

- Age class ( $\leq 17$  years,  $> 17$  years);
- BMI class ( $< 30$  kg/m^2,  $\geq 30$  kg/m^2).

It will be specified in the respective sections which tables will be affected.

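### The BMI subgroup of the responder analysis applies an adult cut of 30 kg/m² to all ages, so its contrast within a cohort may be confounded with age

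*Protocol*

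**What the plan says.** Protocol 3.5 asks for 45 evaluable subjects, 15 in each cohort, and sets two subpopulation targets. One is 14 children, defined as aged 17 or younger and given as 30%. The other is "a target of 9 (20%) obese subjects with BMI of ≥ 30" (in kg/m²), with no reference to age. The same section lets both groups fall across cohorts "without respect to balanced enrollment within the cohorts for these subpopulations". The synopsis repeats this and SAP 4.1 carries the same targets. The inclusion criteria in protocol 4.1.1 give no lower age limit.

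The background uses the cut for adults. Protocol 1.1.4 reports that "in obese adults (body mass index [BMI] ≥ 30 kg/m²) a mean volume per site of 17.8 mL was documented", and protocol 1.1.3 names children and obese adults as two different groups: "manual push is well tolerated in both pediatric and obese adult patients".

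For the analysis, protocol 11.3.5 says "Descriptive subgroup analyses will be performed for Infusion Parameters by" age class (up to 17, over 17) and BMI class (below 30, 30 or more). SAP 8.2.9 lists the same two factors under "The analysis of infusion parameters will be presented stratified by" and adds that no covariates will formally be investigated. SAP 11.1 requests the two subgroup outputs for the primary endpoint (its Table 14.3.2). None of these sections describes BMI class within age class, an adults-only BMI table, or a BMI criterion for children. The table shells are a separate document and were not available.

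**The concern.** A fixed BMI of 30 is hard for a small child to reach. By the SAP 8.2.8 formula, a child 1.20 m tall would have to weigh 30 × 1.20² = 43.2 kg, and one 1.00 m tall 30 kg (heights chosen for illustration). Children will therefore tend to be counted below 30 whatever their build. The lower class would then mix non-obese adults with children, while the upper class would be mostly or wholly adult.

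The sponsor set an enrollment target for obese subjects and a table for them within the primary-endpoint analysis. A reader will use that table to see whether obese subjects reach the higher volumes and flow rates. If children respond at a different rate from adults, a gap between the BMI classes, or the lack of one, could come from age rather than adiposity.

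**Working it through.** **1. The plan's own figure.** With 15 subjects and a true rate of 50%, P(at least 5 responders) = 1 − (1 + 15 + 105 + 455 + 1365)/32768 = 0.9408, which reproduces the stated 94%. BMI class does not enter it.

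**2. Inputs for the age mix.** 45 subjects, 14 children and 9 obese (protocol 3.5). 14/45 = 31.1% and 9/45 = 20.0%, so the stated 30% and 20% refer to 45. The number of children with BMI of 30 or more, c, is not given; it is an assumption, shown as a range.

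**3. Age mix of the BMI classes, all cohorts together.** Share of children below 30 = (14 − c)/36; share at 30 or more = c/9. The last three columns give the apparent BMI difference, (child − adult responder gap) × (difference in shares), when BMI has no effect at all. The gaps of 10, 20 and 30 points are assumptions.

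| c | Children, BMI < 30 | Children, BMI ≥ 30 | Gap 10 | Gap 20 | Gap 30 |
|---|---|---|---|---|---|
| 0 | 14/36 = 38.9% | 0/9 = 0% | 3.9 | 7.8 | 11.7 |
| 1 | 13/36 = 36.1% | 1/9 = 11.1% | 2.5 | 5.0 | 7.5 |
| 2 | 12/36 = 33.3% | 2/9 = 22.2% | 1.1 | 2.2 | 3.3 |
| 3 | 11/36 = 30.6% | 3/9 = 33.3% | −0.3 | −0.6 | −0.8 |

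Exact balance needs c = 14 × 9/45 = 2.8. If the targets are set against the roughly 50 enrolled instead, the c = 0 share is 14/41 = 34.1%.

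**4. Per cohort.** Responder rates are calculated within cohort, and SAP 7 plans no total over cohorts. On average a cohort holds 9/3 = 3 obese subjects, 12 others, and 14/3 = 4.7 children. The mix need not be even. The Volume Cohort requires at least 10 g a week, which means 10,000/200 = 50 kg at 200 mg/kg, or 100 kg at 100 mg/kg. Smaller children would therefore mostly enter the two flow-rate cohorts. If all 14 did, alongside 6 obese adults among 30 subjects (assumption), children would be 14/24 = 58.3% of the class below 30 there.

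**5. Could response depend on age?** Doses of 100 to 200 mg/kg at 200 mg/mL (SAP 11.3) are 0.5 to 1 mL/kg a week: 12.5 to 25 mL at 25 kg and 40 to 80 mL at 80 kg (weights assumed). In the Manual Push Cohort an infusion stays valid if it overruns the calculated time by no more than the larger of 1 minute and 10% (protocol Table 6). At the 2 mL/min level:

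| Volume | Calculated time | Longest valid time | Slowest valid mean rate |
|---|---|---|---|
| 2 mL | 1 min | 2 min | 1.00 mL/min |
| 5 mL | 2.5 min | 3.5 min | 1.43 mL/min |
| 20 mL | 10 min | 11 min | 1.82 mL/min |

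The test is looser for small volumes. A 2 mL infusion can pass at the rate of the level below. This is a route from body size to response in one cohort, not a measured age effect.

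**The case against.** Several counterarguments carry weight.

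- **Confounding is not established.** A reader might infer that the lower class takes in all the children and that the comparison is confounded as a matter of fact. The documents do not support that. A child with BMI of 30 or more counts as obese, the number of such children is not given, and about three would remove the imbalance. Bias also needs response to differ by age, which the documents do not quantify.
- **The volume argument is not uniform.** Protocol 1.1.4 reports a mean of 17.1 mL per site at ages 10 to 18, against 15.8 mL in adults and 17.8 mL in obese adults. Older children did not infuse less per site. The argument is left with smaller children, for whom that section gives no volume.
- **Sparse numbers dominate.** With about 3 obese subjects in a cohort, one responder moves the rate by 33 points, well above the 3.9 to 11.7 points of apparent difference at c = 0. Restricting to adults makes the tables sparser still.
- **The analysis is descriptive.** It is not tested and feeds no decision. Listings carry age and BMI, so a determined reader could cross-classify the subjects by hand.

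All of this limits the consequence. It does not make the planned table interpretable on its face, and readers of a summary table seldom rebuild it from listings.

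**Conclusion.** The point holds as a likely risk, not a certainty. One adult cut is applied to all ages, the age and BMI breakdowns are listed separately, and nothing in the text controls for the age mix of the BMI classes.

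At the targets the imbalance runs from 39% against 0% children (c = 0) to about even (c = 3). The resulting apparent BMI difference is at most about 12 points under the assumed age gaps of up to 30 points, using the study-wide mix; it could be larger in a cohort that enrolls more of the children. The view that few children will reach 30 rests on the height and weight arithmetic and on judgement, not on a figure in the documents.

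A reader might also infer that the label recommendation is at risk. It is not: the success rule uses all subjects in a cohort's Safety Population, and neither the 33% threshold nor the 94% probability depends on BMI class. What is affected is the reading of one descriptive table. The change is still worth making because it is specific and cheap.

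**What to change.** In SAP 8.2.9 and 11.1, and in protocol 11.3.5 for consistency, state that the BMI classes (below 30, and 30 kg/m² or more) are presented among subjects over 17 years, with subjects aged 17 or younger shown in their own column. Adapt the shell for Table 14.3.2 to match.

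The cost is a wording change and one table layout; age and BMI at Screening are already collected. The drawback is a smaller class below 30. With no obese children, the average cohort contrast goes from about 3 against 12 to about 3 against 7 (12 − 4.7 = 7.3), or 9 against 22 study-wide.

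The obese target in protocol 3.5 need not change, and no external growth reference is needed.
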